completion, the sheath is initially pulled by approximately 2 to 3 cm. The device is applied to the patient with the green marker (located in the center of the larger balloon) positioned exactly at the puncture hole to aid in the location, visualization and control of possible bleeding. The balloon is inflated with an adequate syringe injecting 15 ml of air with simultaneous and total sheath removal, resulting in the absence of active bleeding. If bleeding occurs, additional 3 ml of air is injected to obtain complete hemostasis. The device is then slowly deflated to the lowest allowable volume (minimum 7 ml) while maintaining hemostasis. If bleeding occurred, 1 ml of air was reintroduced from the bleeding point. Radial artery patency was evaluated utilizing plethysmographic and pulse oximetry evaluation, with sensor placed over the thumb or index finger, and occlusion (manual pressure) of the ulnar artery. Absence of plethysmographic waveform is indicative of interruption of radial artery flow. After 1 hour post diagnostic procedure or 2 hours post intervention, 3 ml of air is removed every 15 minutes. If bleeding occurs during any stage of device removal, the volume of air needed for hemostasis is again injected, restarting the deflation process 60 minutes later. When all the air is removed, and there is no bleeding, the device is removed and the access site is covered with a simple dressing. Dressing should not encircle the entire wrist.

Statistical analysis

The primary analysis of the study is a superiority comparison between the use of nitroglycerin to decrease RAO, in all randomized patients, based on the intention-to-treat principle.

Using our primary end point to estimate the sample size, we suppose to have a 30% reduction in RAO for each trial intervention, considering potential interaction between them. Estimating RAO prespecified in the primary outcome of approximately 11.7% without use of nitroglycerin, with an alpha level of 0.05 and a beta level of 0.20, the minimum estimated sample size per group was established as 1064 individuals. As we do not expect any subsequent loss of follow-up due to the short primary evaluation, the enrollment of 2128 patients would provide sufficient power to the

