study. Continuous variables will be described as means and standard deviation and compared using Student's t -test for normally distributed variables or assessed using Mann-Whitney test when not normally distributed. Categorical variables are expressed as frequencies and group percentage and will be compared with the chi-square or Fisher's exact tests. To test the interaction between interventions, we used a multivariable logistic-regression model that included the two randomized treatments and their interaction as parameters. In the analysis of the primary and secondary end points, a two-tailed p value of less than 0.05 will be considered statistically significant. No prespecified interim analysis will be performed. All analyses will be performed using SPSS version 22 (SPSS Inc., Chicago, Illinois).

Discussion

Cardiac catheterization is a common procedure and is need in many clinical scenarios and many times repeated procedures are need. The use of TRA is increasing aiming to improve patient comfort, save costs and reduce rates complications. This implies that the occurrence of RAO should be considered because, once it's occurred, it is impossible to use radial access for future catheterization. In most cases RAO occurs promptly after the procedure and up to 50% of patients have spontaneous recanalization of the artery within 1 month. A palpable pulse does not exclude the diagnosis of RAO: collateral blood flow may supply the periphery of the radial artery distally to the occlusion, giving a false impression of radial artery patency. Therefore, RAO can often be undiagnosed. Radial artery patency is better evaluated with clinical testing as the reverse Barbeau's test and with Doppler ultrasonography. Many interventions are suggested to reduce the risk of RAO, mainly anticoagulation, patent hemostasis and a bigger sheath-to-radial-artery ratio. Although nitroglycerin promotes vasodilation and thus improves the sheath-to-radial-artery ratio, no recommendation is done to its routinely use. Handling confounding factors such as anticoagulation and hemostasis, this test has an ideal design to address the question of whether routine use of the

nitroglycerin approach is superior to not use with respect to the occlusion occurrence, including possible predictors.

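### The sample size is said to take account of interaction between the two doses, but 2128 patients include no allowance for it, and a non-significant interaction test would not show that the doses act independently

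*Combined protocol and SAP*

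**What the plan says.** The trial is a 2-by-2 factorial of nitroglycerin or placebo after sheath insertion and again before sheath removal. The end of the Background section gives each dose its own question.

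The Statistical analysis section sets the size as follows:

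- Effect: "we suppose to have a 30% reduction in RAO for each trial intervention, considering potential interaction between them".
- Event rate: "Estimating RAO prespecified in the primary outcome of approximately 11.7% without use of nitroglycerin".
- Error rates: "with an alpha level of 0.05 and a beta level of 0.20". Later in the same section, "a two-tailed p value of less than 0.05 will be considered statistically significant".
- Result: "the minimum estimated sample size per group was established as 1064 individuals".
- Losses: "we do not expect any subsequent loss of follow-up due to the short primary evaluation". The section concludes that "the enrollment of 2128 patients would provide sufficient power to the" study.

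For the interaction itself it says "we used a multivariable logistic-regression model that included the two randomized treatments and their interaction as parameters". It gives no assumed size of interaction, no rates for the four cells, no inflation factor, no power for the interaction test and no rule for what follows from its result.

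**The concern.** The sentence on effect size tells the reader that interaction was taken into account when 80% power was claimed. The total of 2128 is exactly 2 x 1064, which is what a two-group calculation gives when each margin of the factorial is treated as a separate trial.

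Interaction is a realistic possibility here, because the same drug at the same dose goes through the same sheath twice in one procedure. If one injection achieves most of the benefit, the other adds little. Each marginal difference then shrinks, because half of the comparator group has also received nitroglycerin.

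Two things are at stake. The main comparisons may have well under 80% power. And a non-significant interaction test, which is the likely result under several quite different truths, could be taken to mean that each injection works in its own right.

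**Working it through.** **Inputs.** From the Statistical analysis section: 11.7% without nitroglycerin; 30% reduction, read as relative, so 0.7 x 11.7% = 8.19%; two-sided alpha 0.05; power 80%; no losses; 1064 per group. The allocation ratio is not stated. I assume four equal cells, 2128/4 = 532, so that each margin has 2 x 532 = 1064.

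**1. The plan's own figure.** Two-sided pooled formula:

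n = [z(0.975)·√(2p̄(1−p̄)) + z(0.80)·√(p0(1−p0) + p1(1−p1))]² / (p0 − p1)²

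With p0 = 0.117, p1 = 0.0819 and p̄ = 0.09945, this is (0.8295 + 0.3556)² / 0.0351² = 1140 per group.

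Other two-sided versions give 1138 (unpooled), 1133 (arcsine), 1153 (log odds) and 1197 (continuity-corrected). One-sided versions give 898, or 954 with continuity correction. None of these gives 1064. The figure is approached if the treated rate is cut to 8.1% (1080) or the reduction is 31% (1062). At 1064 per group the same formula gives 77.2% power. The stated size is therefore about 7% below the plain two-group size (1064/1140 = 0.933) and contains no increase for interaction.

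**2. Power of the marginal comparisons.** The 11.7% is described as the rate without nitroglycerin, which in this design is the double-placebo cell. Each margin averages two cells. Cells are listed as neither, start only, end only, both.

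| Scenario | Cells (%) | Margins (%) | Power at 1064 per margin |
|---|---|---|---|
| Independent on the odds scale | 11.7 / 8.19 / 8.19 / 5.67 | 9.95 v 6.93 | 71% |
| Each alone gives 30%, second adds nothing | 11.7 / 8.19 / 8.19 / 8.19 | 9.95 v 8.19 | 29% |
| 30% is net, doses fully redundant | 11.7 / 6.3 / 6.3 / 6.3 | 9.0 v 6.3 | 65% |

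For the first row, the joint cell satisfies logit(p11) = 2·logit(0.0819) − logit(0.117), so p11 = 5.67%.

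For the third row, let q be the common rate with any nitroglycerin. A net 30% reduction requires q / [(0.117 + q)/2] = 0.7, so q = (0.7/1.3) x 11.7% = 6.3%. Each dose alone would then have to cut RAO by 46%.

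**3. Power of the planned interaction test.** The parameter is

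log ratio of odds ratios = logit(p11) − logit(p10) − logit(p01) + logit(p00), with SE = √Σ 1/[532·p(1−p)] over the four cells.

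- 11.7/8.19/8.19/8.19%: −2.021 + 2.417 = 0.396, a ratio of 1.49. SE = √(0.0182 + 3 x 0.0250) = 0.305, z = 1.30, power 25% (simulation 25%).
- 11.7/6.3/6.3/6.3%: −2.021 + 2.700 = 0.678, a ratio of 1.97. SE = √(0.0182 + 3 x 0.0318) = 0.337, z = 2.01, power 52%.
- Independent doses: 5%, by construction.

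A non-significant interaction therefore has probability 95% when the doses are independent, 75% in the first redundant case and 48% in the second. It discriminates poorly between them.

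**The case against.** The strongest reply is that the clause on interaction qualifies the 30%, not the sample size. On that reading 30% is what each intervention keeps after any interaction, and what is missing is detail. The wording allows this, and it changes the interaction power: 52% instead of 25% under full redundancy. It does not rescue the size. With 11.7% as the double-placebo rate, marginal power is 65%. Even if 11.7% and 8.19% are taken directly as the marginal rates, 1064 gives 77%.

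It is also fair to say that low power for interaction is normal in a 2-by-2 trial sized on main effects, and is not a defect in itself.

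Three stronger readings are tempting, and the documents do not support them:

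- *That the plan claims power for the interaction test or for one dose against double placebo.* It claims neither. The 1064 is the size of a factorial margin, and no single-dose comparison is planned.
- *That a non-significant interaction is set to license separate claims for each dose.* The plan has no rule on this. The risk comes from that silence together with the separate aims in the Background section.
- *That treatment effects will be taken from the coefficients of the interaction model.* The model is introduced only to test interaction. Categorical outcomes are compared by chi-square or Fisher's exact tests.

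**Conclusion.** The point holds in this form: the sample-size statement refers to interaction, but 2128 makes no allowance for it and falls slightly short even of the plain two-group size (1064 against about 1140, 77% power). Marginal power is about 71%, 65% or 29% in the three scenarios worked through, against a stated 80%. The planned interaction test has 25% or 52% power under full redundancy, so p ≥ 0.05 would not show that the two doses act independently.

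The scenario figures rest on equal allocation to four cells, on 11.7% being the double-placebo rate, and on 30% being a relative reduction. The finding that 1064 contains no allowance needs only the last of these. It would also be wrong to describe the size as one that assumes no interaction: under no interaction on the odds scale it delivers 71%, because the calculation leaves the other factor out altogether.

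**What to change.** No extra patients are needed.

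1. In the Statistical analysis section, replace the clause on potential interaction with: *The size is a two-group calculation that ignores the other factor and makes no allowance for interaction.* Follow it with the marginal powers (77% for the plain comparison; 71%, 29% and 65% in the three scenarios) and the interaction powers (25% and 52%), each with its cell rates and the equal-allocation assumption.
2. State that the two marginal comparisons are primary whatever the interaction p value, and that p ≥ 0.05 is not evidence of no interaction.
3. Report the ratio of odds ratios with its 95% confidence interval, and the four cell rates with 95% confidence intervals. Base any statement about one dose alone, or about both, on these.

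The document is dated December 2024, and its abstract expected inclusion to end in 2019. If outcome data are already known, label the added analyses as post hoc.

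The cost is a few sentences and one four-row table. The stated power becomes less favourable.

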Design and rationale of the Prevention of radial Artery occlusion after Transradial accEss using
NitroglyceriN (PATENS)

NCT03158532

Florianópolis, dec/04/2024

Design and rationale of the Prevention of radial Artery occlusion after Transradial accEss using NitroglyceriN (PATENS)

Abstract

Background

Radial artery occlusion (RAO) is an important access site complications after transradial catheterization (TRC). Acute loss of radial artery patency after TRC is thought be due to a thrombotic process, and a bigger sheath-to-radial-artery ratio could reduce the incidence of RAO. Nitroglycerin acts through the liberation of nitric oxide (NO), which promotes muscle relaxation and vasodilation. Leading to a bigger sheath-to-radial-artery ratio the nitroglycerin administration could help to keep the radial artery patency. The aim is to study if nitroglycerin is superior to placebo concerning incidence of radial artery occlusion, confirmed by vascular Doppler ultrasound, up to 24 hours after catheterization.

Methods/Design

PATENS is a national, multicenter, superiority, 2-by-2 factorial, randomized clinical trial. Two thousand one hundred twenty-eight patients submitted to TRC will be randomized to either nitroglycerin or placebo, administered intra-arterially through the sheath, in two different moments during TRC: after the arterial sheath insertion, at the beginning of procedure, and at the end of the radial procedure, before sheath removal.

Results

The primary efficacy objective is to test the hypothesis that nitroglycerin, dose of 500 mcg, is superior to placebo in decreasing rates of radial artery occlusion on ultrasound Doppler analysis up

to 24 hours after procedures. As secondary objectives, the trial will evaluate the incidence of radial artery occlusion 30 days after catheterization. Enrollment was initiated in August 2017, and the inclusion phase is expected to last until the second half of 2019.

Conclusions

The PATENS trial will help define the role of prophylactic nitroglycerin as a RAO avoidance strategy in patients with submitted to TRC.

Trial registration

ClinicalTrials.gov identifier: NCT03158532

Background

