Acute loss of radial artery patency after cardiac catheterization is thought to be due to a thrombotic process. Sheath insertion leads to local endothelial injury and cessation of blood flow in the radial artery, creating an environment conducive to thrombosis. RAO tends to occur early after transradial catheterization, and roughly 50% of patients have spontaneous recanalization of the artery within 1 month. Direct support for the thrombotic hypothesis has come from recent studies that have confirmed the presence of radial artery thrombus on vascular ultrasound, angiography, and pathology. Transradial catheterization can negatively affect radial artery structure as well. A study using optical coherence tomography found that 67% of radial arteries had intimal tears and 36% had medial dissections immediately after transradial PCI. A study of radial artery function after transradial catheterization found that flow-mediated dilatation was blunted up to 9 weeks. The

radial artery response to nitroglycerin was also decreased, suggesting that the impairment in function was more than just temporary damage to the endothelium and involved long-term changes to the smooth muscle layer.

Nitrates in intra-arterial have been widely studied in prevention of spasm. Nitroglycerin binds to the surface of endothelial cells and undergoes two chemical reductions to form nitric oxide (NO). The nitric oxide then moves out of the endothelial cell and into an adjacent smooth muscle cell, where it promotes the formation of cyclic guanosine monophosphate (cGMP), which promotes muscle relaxation. A bigger sheath-to-radial-artery ratio could reduce the incidence of RAO, indeed current data show that nitroglycerin intra-arterial at the end of the procedure reduce the incidence of radial artery occlusion, so the main objective of this study is to evaluate whether administration of nitroglycerin at the start of a transradial procedure may preserve the patency of the radial artery; as well, confirm if nitroglycerin administration just before sheath removal helps to keep the radial artery patency, probably mediated by vasodilation.

Methods

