This is a randomized, multicenter, double-blind, placebo-controlled phase III study (Clinicaltrials.gov identifier NCT 03158532) with an all-comers design, comparing the use of nitroglycerin to decrease the rate of radial artery occlusion after transradial catheterization. Using a 2-by-2 factorial design, we will randomly assign 2128 patients with a clinical indication for coronary angiography (ad hoc angioplasty allowed) or percutaneous coronary intervention (PCI) to receive either 500 micrograms of nitroglycerin or placebo (0,9% sodium chloride), administered intra-arterially through the sheath, in two different moments during transradial catheterization: shortly after the arterial sheath insertion and at the end of the radial procedure, before sheath removal. Written, informed consent will be obtained from each subject. The study protocol has been presented to the institutional medical ethical committee of all participating hospitals to comply with local standards.

Randomization and final acceptance into the study will take place after successful radial artery cannulation and guide wire advanced into the radial arterial lumen through the needle to allow exclusion of failed radial puncture.

Patient population

All eligible patients are aged 18 years or over with a clinical indication for coronary angiography (ad hoc angioplasty was allowed) or percutaneous coronary intervention (PCI) if the following pre-requisites are met: (i) choice of the operator to use the transradial access route and (ii) use of sheath size 5 or 6 French. Allen test was not obligatory performed. The exclusion criteria were: (I) primary angioplasty due to acute myocardial infarction; (ii) intubated patients; (iii) complications during procedure (cardiac arrest, pulmonary oedema, cardiogenic shock, and stroke); (iv) prior inclusion in this trial; (v) known allergy or intolerance to nitrates; (vi) patients medicated with continuous intravenous nitrates or whom received any nitrates on the last hour and (vii) use within 24 hours prior to randomization of phosphodiesterase inhibitors.

Outcomes

Primary outcome

RAO: incidence of radial artery occlusion as confirmed by the absence of antegrade flow in vascular high resolution duplex ultrasound, up to 24 hours after catheterization.

Secondary outcomes

Late RAO: incidence of radial artery occlusion as confirmed by the absence of antegrade flow in vascular high resolution duplex ultrasound, 30 days after catheterization.

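### The sample size takes 11.7% as the control rate, but if both doses work each placebo margin sits near 9.9%, so power per margin is about 70% under proportional effects (range 29% to 84%), not 80%

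*Combined protocol and SAP*

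**What the plan says.** The Methods section describes a 2-by-2 factorial trial of 2128 patients. Each patient receives 500 micrograms of nitroglycerin or placebo, "administered intra-arterially through the sheath, in two different moments during transradial catheterization": after sheath insertion and before sheath removal. No allocation ratio is stated.

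The Statistical analysis section takes its control rate as follows: "Estimating RAO prespecified in the primary outcome of approximately 11.7% without use of nitroglycerin". On the effect it says "we suppose to have a 30% reduction in RAO for each trial intervention, considering potential interaction between them". With alpha 0.05 and beta 0.20, "the minimum estimated sample size per group was established as 1064 individuals". It gives no expected rate for any of the four cells or for either margin, and no size for the interaction. It calls the primary analysis a superiority comparison in all randomized patients but does not say which factorial contrast is meant. On interaction it says: "To test the interaction between interventions, we used a multivariable logistic-regression model that included the two randomized treatments and their interaction as parameters". No rule follows from the result of that test.

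The question is worded in three ways:

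- **Abstract:** "nitroglycerin, dose of 500 mcg, is superior to placebo in decreasing rates of radial artery occlusion", with no timing.
- **Background:** by timing. The start dose is the main objective, and the trial should also "confirm if nitroglycerin administration just before sheath removal helps to keep the radial artery patency".
- **Discussion:** whether the "nitroglycerin approach is superior to not use with respect to the occlusion occurrence".

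**The concern.** Since 2 × 1064 = 2128, a group can only be a margin: everyone randomized to nitroglycerin at one time point against everyone randomized to placebo at that time point. The 11.7% rate describes patients with no nitroglycerin at all, which in this design is one cell of four. The other half of each placebo margin is randomized to nitroglycerin at the other time point. If that dose works, as the plan assumes, the margin's event rate is below 11.7%, and the stated power does not belong to the comparison that will be made.

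Two things are at stake. The first is the 80% figure itself, which readers will use to judge a non-significant margin. The second is interpretation. Because the primary contrast is not named, a conclusion about using nitroglycerin versus not using it could be drawn from a margin whose control group is half nitroglycerin.

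**Working it through.** **Inputs from the Statistical analysis and Methods sections.** Rate with no nitroglycerin 11.7%; 30% reduction per intervention, so 0.7 × 11.7% = 8.19%; two-sided alpha 0.05; power 80%; 1064 per group; 2128 in total; no loss to follow-up.

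**Assumptions.** Equal allocation (2128/4 = 532 per cell); each dose alone gives 8.19%; the rate with both doses is varied, because the documents do not give it.

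**Step 1: the plan's own figure.** With p̄ the mean of p₁ and p₂,

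n = [1.960·√(2p̄(1−p̄)) + 0.842·√(p₁(1−p₁) + p₂(1−p₂))]² / (p₁−p₂)².

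For 11.7% versus 8.19% this gives 1140 per group. A continuity correction gives 1197, unpooled variance 1138, the arcsine method 1133 and a one-sided test 898. None reproduces 1064.

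Power at n = 1064 is Φ[(|p₁−p₂| − 1.960·SE₀)/SE₁], where SE₀ = √(2p̄(1−p̄)/n) and SE₁ = √((p₁(1−p₁) + p₂(1−p₂))/n). For 11.7% versus 8.19%: SE₀ = 0.01297, SE₁ = 0.01295, and (0.0351 − 0.0254)/0.01295 = 0.75, so power is 77%. This shortfall exists before any overlap between doses.

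**Step 2: the marginal control rate.** The placebo margin averages the neither-dose cell and the cell given only the other dose: (11.7% + 8.19%)/2 = 9.945%.

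**Step 3: the active margin and its power.** The active margin is (8.19% + both-dose rate)/2. The same formula at 1064 per margin gives:

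| Joint effect | Both doses | Active margin | Difference from 9.945% (points) | Relative reduction | Power | n per margin for 80% |
|---|---|---|---|---|---|---|
| Additive in risk | 4.68% | 6.435% | 3.51 | 35% | 84% | 957 |
| Proportional (0.7 × 0.7) | 5.73% | 6.96% | 2.98 | 30% | 70% | 1364 |
| Half the proportional extra effect | 6.96% | 7.58% | 2.37 | 24% | 49% | 2235 |
| No extra effect | 8.19% | 8.19% | 1.76 | 18% | 29% | 4202 |

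For the proportional row, SE₀ = 0.01206, SE₁ = 0.01204, and (0.02984 − 0.02364)/0.01204 = 0.51, so power is 70%. Simulation with cells of 532 agrees for the additive, proportional and no-extra rows (84%, 70%, 29%). If only one dose works, its margin is 11.7% versus 8.19%, with 77% power.

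**Step 4: would the interaction test give warning?** On the logit scale the standard error of the interaction is √Σ[1/(532·p(1−p))] over the four cells. With no extra effect, the interaction is 0.396 with standard error 0.305, so power is 25%. The other rows give 9% (additive), 5% (proportional) and 11% (half extra). A non-significant result says little about whether the margins can be read on their own.

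**The case against.** The strongest reply is that nothing is wrong with the margins. The Background states the main objective by timing, and the sample-size text powers each intervention. For that question the margin is the standard factorial contrast. Under proportional effects it shows exactly the planned 30% relative reduction, and under additivity it shows the full 3.51 points of that dose at 84% power. This stands, and it is why the margins should remain primary.

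A reader might go further and infer that the trial understates the benefit of nitroglycerin, because a margin shows only 50% to 75% of the absolute difference between any use and none. The documents do not support that as a defect. It needs the question to be any use versus none, which rests mainly on one Discussion sentence that defines no analysis; the Abstract is silent on timing. It also applies only to the absolute scale, whereas the plan's effect is relative.

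A reader might also take 29% as the expected power, or cite the 51% chance that neither margin is significant. Both belong to the case where the second dose adds exactly nothing, which no section states. The chance that neither is significant is 9% under proportional effects and 2% under additivity.

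Three further points stand. The gap between 1140 and 1064 is a separate error and not evidence about overlap. The planned logistic model already yields start-only and end-only versus neither, as odds ratios. A pooled contrast of three cells against one (1596 versus 532) mixes one dose with two and has only 35% power if one dose works, so it is an option and not a correction.

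None of this restores 11.7% as the marginal control rate when both doses work.

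**Conclusion.** The concern holds as a mismatch between the planning rate and the comparison being powered. If both doses work as assumed, the marginal control rate is 9.945% and not 11.7%. Power per margin is about 70% under proportional effects, within a range of 29% to 84%. The planned 80% is reached only when the joint effect is close to additive. The plan says interaction was considered but shows no figure for it, and 1064 falls short (77%) even with no overlap.

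The result rests on equal cells, on a 30% reduction from each dose alone, and on a joint effect between none extra and additive. It does not show that the marginal tests are invalid or that the trial is bound to miss an effect. A margin does not by itself support a statement that nitroglycerin is superior to non-use, since half of its control group is randomized to nitroglycerin.

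**What to change.** In the Statistical analysis section:

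1. Name two primary comparisons, start dose versus start placebo and end dose versus end placebo, each 1064 versus 1064 in all randomized patients. Align the Abstract with this; the Background already frames the question so.
2. State the four assumed cell rates and restate power per margin from the marginal control rate: about 70% if effects are proportional, with the range, in place of 80%. Correct or explain 1064 against the 1140 that the plan's inputs give.
3. Report the four cell rates, and start-only, end-only and both versus neither, each with a 95% confidence interval, whatever the interaction p-value.
4. Rest any statement of superiority over non-use on those comparisons with the neither-dose cell, labelled secondary. The Abstract expected inclusion to run to the second half of 2019 and the document is dated December 2024, so label them post hoc if they are specified after the data are seen. Note that the Transradial procedure section leaves additional vasodilators to the operator, so this cell is placebo-placebo as randomized and not necessarily free of nitroglycerin.

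A pooled three-cells-versus-neither contrast may be added but is not required.

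The cost is revised text and one four-cell table from data the trial already collects. The marginal tests do not change and lose no power. No added enrolment is asked for; reaching 80% under proportional effects would take 2 × 1364 = 2728 patients, 600 more than planned, so the honest course is to state the lower power.

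### The stated 1064 per group does not follow from the plan's own inputs; on those inputs power is about 77%, not 80%

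*Combined protocol and SAP*

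**What the plan says.** The sample-size paragraph in the protocol's Statistical analysis section gives the effect as "we suppose to have a 30% reduction in RAO for each trial intervention", with the qualifier "considering potential interaction between them". It puts the RAO rate at "approximately 11.7% without use of nitroglycerin, with an alpha level of 0.05 and a beta level of 0.20". It then says that "the minimum estimated sample size per group was established as 1064 individuals", allows for no loss to follow-up, and concludes that 2128 patients give enough power.

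The same section names chi-square or Fisher's exact tests for categorical variables and sets the significance rule for primary and secondary endpoints: "a two-tailed p value of less than 0.05 will be considered statistically significant". The Methods section confirms the total: "Using a 2-by-2 factorial design, we will randomly assign 2128 patients". Since 2128 = 2 × 1064, a group here is one side of a factor margin (nitroglycerin versus placebo at one time point), not one of the four factorial cells. No sample-size formula or software procedure is named, and no figure is attached to the interaction.

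**The concern.** The paragraph gives a control rate, a relative reduction, alpha, beta and a zero loss rate, and the analysis text supplies the sidedness. A reader can therefore repeat the calculation, and it does not return 1064. The stated number is too small for every two-sided method tried and too large for the one-sided ones, so it is not simply a different choice of formula.

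The number is called a minimum for beta 0.20. If beta is larger on the plan's own assumptions, a non-significant result would be read against a type II error that the design does not have. There is no margin to absorb the difference, because the total is exactly twice 1064 and no allowance is made for losses.

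**Working it through.** **Inputs, all from the Statistical analysis section**

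- Control rate p1 = 0.117.
- Reduction of 30%, read as relative: p2 = 0.117 × 0.70 = 0.0819.
- Difference d = 0.0351; mean rate p̄ = (0.117 + 0.0819)/2 = 0.09945.
- Two-sided alpha 0.05: z = 1.960. Beta 0.20: z = 0.842.
- Equal groups, no losses.

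**Attempt to reproduce 1064**

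Pooled-variance formula: n = [1.960 √(2p̄(1 − p̄)) + 0.842 √(p1(1 − p1) + p2(1 − p2))]² / d².

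- 2p̄(1 − p̄) = 0.17912; 1.960 × √0.17912 = 0.8295.
- p1(1 − p1) + p2(1 − p2) = 0.10331 + 0.07519 = 0.17850; 0.842 × √0.17850 = 0.3556.
- n = (0.8295 + 0.3556)² / 0.0351² = 1.40443 / 0.00123201 = 1139.95, so **1140**.

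Other methods, same inputs:

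| Method | n per group |
|---|---|
| Unpooled: (1.960 + 0.842)² × 0.17850 / d² = 1137.2 | 1138 |
| Arcsine: 2 × (1.960 + 0.842)² / 0.11772² = 1132.7 | 1133 |
| Log odds ratio | 1153 |
| Log risk ratio | 1158 |
| Continuity-corrected: (n/4)[1 + √(1 + 4/(nd))]² with n = 1139.95, giving 1196.3 | 1197 |
| One-sided pooled | 898 |
| One-sided, continuity-corrected | 954 |

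None gives 1064, and none is within 3% of it (about 1033 to 1095).

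**Power at 1064 per group**

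Power = Φ{[d√1064 − 0.8295] / √0.17850} = Φ{(1.1449 − 0.8295)/0.4225} = Φ(0.747) = **77.2%**, so beta = 0.228. Other two-sided versions give 77.3% (unpooled), 77.5% (arcsine), 77.4% (exact enumeration of the chi-square test) and 75.3% (Fisher's exact). One-sided power would be 85.6%.

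**Size of the gap**

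1140 − 1064 = 76 per group, and 76/1064 = 7.1%. In total, 2280 − 2128 = 152. A 31% reduction (11.7% to 8.07%) needs 1062 per group, so 1064 gives 80% power for that effect.

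**Could rounding or the factorial structure explain it?**

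- Control rate anywhere from 11.65% to 11.75%: 1146 to 1135. Getting near 1064 takes 12.4% (1069) to 12.5% (1059).
- Treated rate rounded to 8.2%: 1147. At 8.1%: 1080 (1135 corrected). At 8.0%: 1018 (1071 corrected). The last two are reductions of 30.8% and 31.6%.
- Factorial margins: suppose 11.7% is the rate with no nitroglycerin at either time and the two effects multiply (an assumption). The control margin is then 11.7% × (1 + 0.70)/2 = 9.945% and the treated margin 9.945% × 0.70 = 6.96%. That needs 1364 per group, and power at 1064 is 69.7%. This moves the requirement further from 1064.
- With a 30% reduction, the continuity-corrected number for 13.0% versus 9.1% is 1064. The documents mention no 13.0%, and other pairs come equally close (for example 11.5% with a 32% reduction, corrected, 1064.05), so the match shows only that different inputs could have been used.

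**The case against.** The strongest reply is that the documents do not give a complete recipe. They name no formula, call 11.7% approximate, refer to an interaction without quantifying it, and state two-tailed testing for the analysis rather than in the sample-size sentence. On this view one can say only that 1064 is not reproducible. The 77% is also conditional: it takes 11.7% as the control rate at each factor margin, although half of each margin's control group receives nitroglycerin at the other time point. Lastly, the gap is small for a planning rate of this kind: power at 1064 is 78.4% if the control rate is 12.0% and about 80% at 12.5%.

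Part of this stands. The 77% must be tied to its rates, the 13.0% explanation is unproven, and the shortfall is modest. None of it rescues 1064. Rounding of 11.7% does not reach it, one-sided testing undershoots it, and the multiplicative factorial reading raises the required number. If an unstated rate or allowance was used, the inputs printed in the paragraph are not those behind its result, and the paragraph still needs correcting. Restating the effect as 31% does fit an effect to a fixed sample size, so it should be worded as what 2128 patients can detect and not as the planning assumption.

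**Conclusion.** The concern holds. For 11.7% versus 8.19%, two-sided alpha 0.05 and 80% power, the requirement is 1140 per group (1133 to 1158 across uncorrected methods, 1197 with continuity correction), against the stated 1064. Power at 1064 is 77.2%, or about 75% with Fisher's exact test, compared with the 80% implied by beta 0.20.

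This rests on reading the 30% as relative, on equal allocation at each margin, on no losses, and on 11.7% being the control rate at the margin. Under the multiplicative factorial reading the shortfall is larger, with power near 70%. The type I error and the planned analysis are unaffected; what is wrong is the stated operating characteristic for the primary endpoint.

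**What to change.** Keep 2128 patients and replace the sample-size sentence with one that names the rates at each factor margin, the sidedness, the formula and the resulting power. Any of the following would do:

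- State that 1064 per margin gives about 77% two-sided power for 11.7% versus 8.19%.
- State that 1064 per margin gives 80% power for a reduction of about 31% (11.7% to 8.07%).
- If another control rate, effect or correction produced 1064, state it and the formula.

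Whichever is chosen, say whether 11.7% is the rate with no nitroglycerin at all or the control rate at each margin, since the power figure depends on it. The cost is one sentence and a slightly less favourable power statement. No patients are added and no trial procedure changes.
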